6.3. Unscheduled Visits

The parent(s)/legal guardian will be requested to contact the study staff if the subject experiences a severe redness or swelling at the injection site (>14 caliper units) or a temperature $\geq 39.0^{\circ}$ C (102.2° F) in the 7 days after vaccination. If the parent(s)/legal guardian does not contact the site, the investigator is required to contact the parent(s)/legal guardian as soon as possible. The outcome of any contact will be recorded on the CRF. The investigator should determine if the subject requires an unscheduled visit. If the unscheduled visit does not take place following subject report of fever $\geq 39.0^{\circ}$ C (102.2° F) or severe redness/swelling, the reason must be documented in the CRF (for example, reaction no longer present or e-diary–entry error).

If the reaction exceeds the maximum size the caliper is able to measure (>14 caliper units), ensure the subject's parent(s)/legal guardian has also measured the maximum diameter of the redness and/or swelling at the injection site using the measuring tape/ruler provided. Ask the subject's parent(s)/legal guardian to report the maximum diameter of the redness and/or swelling at the injection site daily until the reaction becomes ≤ 14 caliper units. Record these measurements in the CRF.

At an unscheduled visit, the subject's axillary temperature should be measured and the symptom that prompted the visit should be assessed by a medically qualified member of the study staff. Findings will be recorded on the CRF including route temperature was taken. If the subject experiences any AEs, these should be recorded on the AE page.

Final Protocol Amendment 2, 19 April 2016

For the purpose of assessments performed during unscheduled visits, a medically qualified member of the study staff is a study physician or a study nurse, as applicable to the investigator's local practice.

6.4. Subject Withdrawal

The investigator and/or sponsor may withdraw a subject from the study if deemed appropriate at any time. Eligibility criteria as listed under inclusion criteria (Section 4.1) and exclusion criteria (Section 4.2) should be taken into consideration when determining if a subject must be withdrawn. The investigator is not required to repeat the physical examination completed at Visit 1, unless clinically indicated.

Reasons why a subject may discontinue or be withdrawn from the study include, but are not limited to, AE (including any neuroinflammatory and autoimmune conditions, such as transverse myelitis, uveitis, optic neuritis, and multiple sclerosis), parent(s)/legal guardian or subject request, investigator request, death, discontinuation of the study by the sponsor, protocol violation, and being lost to follow-up.

An effort must be made to determine why a subject fails to return for the necessary visits or is withdrawn from the study. Information detailing the circumstances leading to the withdrawal of a subject from the study, as well as the date of withdrawal, will be recorded on the study-outcome CRF.

The decision to withdraw a subject from the study should be discussed with the sponsor. Every attempt must be made to collect all prompted reactogenicity data, AEs, or SAEs following each vaccination. Any AEs or SAEs that are continuing at the time of withdrawal from the study must be followed until the events have subsided, returned to baseline, or in case of permanent impairment, until the condition stabilizes.

When a subject discontinues or is withdrawn from the study prior to completion, the investigator will notify the sponsor and, when possible, will perform the procedures indicated in Section 6.1.11 (discontinued sentinel subjects) or Section 6.1.12 (subjects who withdraw prior to Visit 8) if the subject has received at least 1 study vaccination.

Subjects may be withdrawn from the study at any time at the request of their parent(s)/legal guardian, or they may be withdrawn at any time at the discretion of the investigator or sponsor for safety or behavioral reasons, or the inability of the subject to comply with the protocol-required schedule of study visits or procedures at a given study site.

If a subject does not return for a scheduled visit, every effort should be made to contact the subject's parent(s)/legal guardian. Details for contacting lost-to-follow-up subjects are provided in the SRM. In any circumstance, every effort should be made to document subject outcome, if possible. The investigator should inquire about the reason for withdrawal, request that the subject's parent(s)/legal guardian return the e-diary (if applicable), request that the subject return for a final visit, if applicable, and follow up with the subject's parent(s)/legal guardian regarding any unresolved AEs.

Final Protocol Amendment 2, 19 April 2016

If the parent(s)/legal guardian withdraws the subject from the study, and also withdraws consent for disclosure of future information, no further evaluations should be performed, and no additional data should be collected. The sponsor may retain and continue to use any data collected before such withdrawal of consent.

7. ASSESSMENTS

Every effort should be made to ensure that the protocol-required tests and procedures are completed as described. However, it is anticipated that from time to time there may be circumstances outside of the control of the investigator that may make it unfeasible to perform the test. In these cases, the investigator will take all steps necessary to ensure the safety and well-being of the subject. When a protocol-required test cannot be performed, the investigator will document the reason for this and any corrective and preventive actions that he or she has taken to ensure that normal processes are adhered to as soon as possible. The study team will be informed of these incidents in a timely fashion.

7.1. Immunogenicity

7.1.1. Blood Draw Volume

Stage 1

To facilitate immunogenicity analysis, subjects will have approximately 5 mL of blood collected at the following time points during Stage 1:

- Immediately before Vaccination 1;
- 1 Month after Vaccination 2;
- 1 Month after Vaccination 3;
- 6 Months after Vaccination 3;
- 12 Months after Vaccination 3.

In total, 25 mL will be collected over the 18-month period. Local/topical anesthetic may be used prior to blood draws.

Stage 2

To determine duration of immune response, Stage 2 subjects will have approximately 5 mL of blood collected at the following time points:

- 2 Years after Vaccination 3;
- 3 Years after Vaccination 3;
- 4 Years after Vaccination 3.

Final Protocol Amendment 2, 19 April 2016

In total, 15 mL will be collected over approximately 2.5 years. Local/topical anesthetic may be used prior to blood draws.

7.1.2. Serum Sample Storage

All serum samples should be stored in an upright position in a laboratory-grade manual-defrost freezer that does not cycle and forms ice that must be removed (a non-frost-free freezer), and that maintains a temperature of -15° C or lower.

It is the responsibility of the investigator(s) (or designee) to record daily freezer temperature readings, to maintain a daily temperature log for the freezer, and to alert the sponsor of any deviations. Deviations from storage requirements, including any actions taken, must be documented and reported to the sponsor. Guidance on sample collection, storage, shipping, temperature monitoring, and procedures for the review of temperature deviations will be provided in the SRM.

CCI

7.1.4. Additional Assays

7.2. Safety

Any subject who receives at least 1 dose of investigational product will be included in the evaluation for safety. The following safety parameters will be assessed as described in the Study Procedures (Section 6) and the Schedule of Activities:

7.2.1. Physical Examination

The subject's medical history, physical examination, and vital signs should be obtained and documented at Visit 1 to capture baseline information and should include the following as a minimum:

- Vaccination history, past and present medical and surgical history of significance, and allergies. When taking the medical history, particular care must be taken to note any neuroinflammatory and autoimmune conditions, such as transverse myelitis, uveitis, optic neuritis, and multiple sclerosis.
- Weight, height (or length for nonwalking subjects), general appearance, skin, head, eyes, ears, nose, throat, heart, lungs, abdomen, extremities, neurologic status, musculoskeletal, and lymph nodes will be assessed. Significant observations from the physical examination will be documented in the CRF.

7.2.1.1. Brief Physical Examination

At vaccination Visits 4 and 6, as well as discontinued sentinel subject/cohort visits (Section 6.1.11), a brief physical examination of the subject's general appearance, ears, throat, heart, and lungs should be performed. Temperature, heart rate, and respiratory rate should also be measured and recorded. Record the route by which the temperature was taken.

7.2.2. Reactogenicity (Prompted Diary/E-Diary Events)

The safety parameters include reactogenicity, ie, both local reactions and systemic events that occur in the 7 days (Days 1 to 7) after investigational product administration. These prospectively collected events are considered prompted diary/e-diary events and include the following:

Final Protocol Amendment 2, 19 April 2016

- Local reactions at the site of investigational product administration (redness, swelling, and tenderness).
- Systemic events (fever, loss of or decreased appetite, drowsiness [increased sleep], and irritability [fussiness]).

Local reactions, systemic events, and use and type of antipyretic medication will be collected using an e-diary. For events that resolve after Day 7, the end date will be collected on the Symptom Resolved Date CRF. If the diary is not completed for 7 days, the end dates for events ongoing on the last day the diary was completed will be collected on the Symptom Resolved Date CRF.

7.3. Electronic Diary

The subject's parent(s)/legal guardian will be issued an e-diary, based on a personal digital assistant (PDA) or equivalent technology. They will be asked to monitor and record local reactions, systemic events, and the use and type of antipyretic medication on the day of vaccination and for 7 days following each vaccination. The e-diary allows recording of these assessments only within a fixed time window, thus providing the accurate representation of the subject's experience at that time. Only the most severe rating for any of the local reactions or systemic events each day will be recorded in the e-diary. End dates of local reactions, systemic events, or use of antipyretic medications that was ongoing on the last day the diary was completed by the parent(s)/legal guardian will be collected on the CRF.

The investigator or designee must contact the parent(s)/legal guardian in order to obtain stop dates for any prompted diary/e-diary events or other AE data ongoing on the last day that the e-diary was completed. The stop dates are to be documented in the source documents and the information entered in the CRF. Data reported in the e-diary will be transferred electronically to the e-diary vendor (a trusted third party), where they will be available for review by investigators at all times via an Internet-based portal. At intervals agreed upon between the vendor and Pfizer, these data will be transferred electronically into Pfizer's database for analysis and reporting. These data do not need to be reported by the investigator on the CRF.

Investigators will be required to review the e-diary data online at frequent intervals as part of the ongoing safety review and evaluation of subject compliance. For sentinel-cohort subjects, following Vaccination 1 online review must be performed daily (see Section 7.9 Stopping Rules).

7.4. Local Reactions

7.4.1. Injection Site Redness and Swelling

Redness and swelling will be measured and recorded in caliper units (range: 1 to 14) for the first 7 days following vaccination (Days 1 to 7), and then categorized using the scale shown in Table 7. The measurements will then be recorded in the e-diary.

B1971035 Final Protocol Amendment 2, 19 April 2016

A caliper will be given to the subject's parent(s)/legal guardian with instructions for measuring both redness and swelling at the injection site. Each caliper unit is equivalent to 0.5 cm. The parent(s)/legal guardian will be asked to measure the largest diameters of the local reaction. Where a caliper measurement is between 2 values, the higher value should be reported. At the time of entry into the e-diary, the parent(s)/legal guardian should record the maximum severity of the reaction since the previous entry into the e-diary. In the event the reaction exceeds the maximum size the caliper is able to measure (>14 caliper units), the subject's parent(s)/legal guardian will also measure the maximum diameter of the redness and/or swelling at the injection site using the measuring tape provided and report this immediately to the investigator. The subject's parent(s)/legal guardian will report the maximum diameter of the redness and/or swelling at the injection site to the investigator daily until the reaction becomes ≤14 caliper units. These measurements will be recorded in the CRF.

Table 7. Grading of Redness and Swelling

Mild	0.5 to 2.0 cm (1 to 4 caliper units)	
Moderate	2.5 to 7.0 cm (5 to 14 caliper units)	
Severe	>7.0 cm (>14 caliper units)	

7.4.2. Injection Site Tenderness

The parent(s)/legal guardian will be asked to assess whether tenderness is present at the injection site for the first 7 days following vaccination (Day 1 to Day 7) and grade it using the Grading of Tenderness, Table 8. The assessment will then be recorded in the e-diary.

Table 8. Grading of Tenderness

Mild	Hurts if gently touched (eg, subject whimpers, winces, protests, or withdraws)	
Moderate	Hurts if gently touched with crying	
Severe	Causes limitation of limb movement	

7.5. Systemic Events

7.5.1. Temperature

A digital thermometer will be given to the subject's parent(s)/legal guardian with instructions on how to measure the child's axillary temperature at home. Axillary temperature will be collected at evening bedtime daily for 7 days (Day 1 to Day 7) after each vaccination, and at any time during the 7 days when fever is suspected. The highest temperature for each day will be recorded in the e-diary. Fever is defined as a temperature of ≥38.0°C (100.4°F).

Temperature will be measured and recorded to 1 decimal place and then categorized according to the Scale for Fever, Table 9:

Final Protocol Amendment 2, 19 April 2016

Table 9. Scale for Fever

Temperature 38.0°C to 38.4°C (100.4°F to 101.1°F)		
Temperature 38.5°C to 38.9°C (101.2°F to 102.0°F)		
Temperature 39.0 °C to 39.4 °C (102.2 °F to 103.0 °F)		
Temperature 39.5°C to 40.0°C (103.1°F to 104.0 °F)		
Temperature >40.0°C (>104.0°F)		

7.5.2. Other Systemic Events

The e-diary will be used to record the presence of other systemic events, including loss of or decreased appetite, drowsiness, and irritability daily for 7 days (Day 1 to Day 7) after each vaccination, using Grading of Other Systemic Events, Table 10.

Table 10. Grading of Other Systemic Events

	GRADE 1	GRADE 2	GRADE 3
	(mild)	(moderate)	(severe)
Loss of appetite	Decreased interest in	Decreased oral intake	Refusal to feed
or decreased appetite	eating		
Drowsiness	Increased or prolonged	Slightly subdued	Disabling not interested in
(synonym with	sleeping bouts	interfering with	usual daily activity
increased sleep)		daily activity	
Irritability (synonym with	Easily consolable	Requiring	Inconsolable;
fussiness, restless sleep;		increased attention	crying cannot
decreased sleep)			be comforted

7.5.3. Use of Antipyretic Medication

The use and type of antipyretic medication will be recorded in the e-diary daily during the active safety observation periods (Day 1 to Day 7) after each vaccination.

For the duration of the vaccination phase of Stage 1 (through Visit 7), prophylactic use of antipyretics and other pain medications to prevent symptoms that might occur as a result of study vaccination is not permitted.

On the day of planned vaccination, if the subject has received antipyretics and other pain medications, vaccination should be temporarily delayed as specified in Section 4.3.

Use of antipyretic and other pain medications following investigational product administration to treat symptoms is permitted.

Please refer to the SRM for further details.

B1971035

Final Protocol Amendment 2, 19 April 2016

7.6. Other Safety Monitoring

7.6.1. Adverse Events

AEs and SAEs reported outside of the e-diary are recorded and reported as described in Section 8.

7.6.2. Immediate Adverse Events

Immediate AEs, defined as AEs occurring within the first 30 minutes after investigational product administration, will be assessed and documented in the AE CRF. The time of onset will be recorded for any AEs that occur on the same day as investigational product administration.

7.6.3. Medically Attended Events and Newly Diagnosed Chronic Medical Conditions

MAEs and NDCMCs will be assessed throughout the vaccination period and up to Visit 8 (Month 12; 6-month follow-up visit) after the last study vaccination.

A medically attended event is defined as a nonserious AE that results in an evaluation at a medical facility.

A newly diagnosed chronic medical condition is defined as a disease or medical condition, not previously identified, that is expected to be persistent or otherwise long-lasting in its effects. This includes conditions that are undiagnosed prior to study entry (diagnosed while on the study) and that are not considered temporary conditions based upon the expected natural history of the condition.

7.6.4. Routine Medical Facility Visits, Elective Hospitalizations, and Routine Concomitant Medication Use Not Associated With Adverse Events

Routine visits to medical facilities and elective hospitalizations not associated with an AE, (ie, health care visits for preventive care, or for routine physical examinations), will not be collected. Non–AE-related concomitant medications other than vaccinations will not be collected. A study visit AE checklist will be used as a guide, completed at each scheduled study visit and telephone visit in Stage 1, and included in the source documentation. Please refer to the SRM for details.

7.6.5. Subject Memory Aid

The parent(s)/legal guardian will be given a memory aid at Visit 7 and as required thereafter. The memory aid will be used as a reminder to review with study site personnel any significant illnesses, hospitalizations, NDCMCs, or visits to a medical facility. At Visits 8, 9, 11, and 12, the memory aid will serve as a reminder to review AEs and RRIs occurring within 48 hours following a blood draw. The parent(s)/legal guardian may use the memory aid as needed during subsequent visits to prompt recall of events. These may be used to assist in reporting and discussion of events with study staff, but these memory aids will not be considered source documents and will not be collected at study visits. Only information

B1971035

Final Protocol Amendment 2, 19 April 2016

collected by study staff as part of the study visits will be included in the source documents and entered into the CRF.

7.7. Sentinel-Cohort Safety Assessments

Post–Vaccination 1, 7-day e-diary and AE data will be collected for each sentinel cohort receiving the 60-µg dose level of bivalent rLP2086. The sentinel data will be reviewed (independently of the other sentinel cohort) by the sponsor's IRC to determine whether the 60-µg dose level presents satisfactory safety, reactogenicity, and tolerability data in the age stratum under review. Based on the review, the decision to commence enrollment in the 120-µg bivalent rLP2086 sentinel cohort for that age stratum will be made and the investigators will be notified accordingly. Enrollment procedural guidance will be addressed in the SRM.

The EDMC will not participate in the dose-escalation or selected dose-level decision-making processes, but will participate in the stopping rule and overall safety data processes, in line with the remit of the EDMC charter.

7.8. Biological Samples

Serum samples will be used only for scientific research. Each sample will be labeled with a code so that the laboratory personnel testing the samples will not know the subject's identity. Some of the samples may be stored by Pfizer for additional testing. The samples will not be used for any unrelated research, and no genetic testing will be performed. The samples will be stored for up to 15 years after the end of the study and then destroyed.

The parent(s)/legal guardian may request that his or her child's samples, if still identifiable, be destroyed at any time; however, any data already collected from those samples will still be used for this research. The biological samples may be shared with other researchers as long as confidentiality is maintained.

7.9. Stopping Rules

The study stopping rules (excluding deaths) apply to bivalent rLP2086–vaccinated sentinel-cohort subjects for the post–Vaccination 1, 7-day safety period only.

Post–Vaccination 1, 7-day e-diary and AE (including deaths) data will be monitored daily during the post–Vaccination 1, 7-day safety period (including non–business days) by the investigator (or medically qualified designee) and sponsor in order to promptly identify and flag any case that potentially contributes to a stopping rule.

Cases that potentially meet stopping rule criteria will be promptly referred to the IRC for rapid evaluation. The IRC will review the case safety data and determine whether or not the case meets a stopping rule. The IRC opinion on study progression will be forwarded to the EDMC.

B1971035

Final Protocol Amendment 2, 19 April 2016

In the event that the IRC confirms that a stopping rule has been met, the following criteria will apply:

- The dose level affected by the stopping rule will PAUSE enrollment and vaccination in both sentinel age groups.
- No further study vaccinations will be administered to any subject in the PAUSED sentinel cohorts until directed to do so.
- The EDMC will convene to evaluate all available safety data and provide its recommendations to the IRC.
- For all sentinel subjects affected by a pause, all other routine study conduct activities such as ongoing data entry, reporting of AEs, subject e-diary completion, and subject follow-up, will continue during the pause.

A stopping rule will be met under the following circumstances:

- Where 2 or more subjects within an age-stratified sentinel cohort receiving the same dose level (60 μg or 120 μg) of bivalent rLP2086 develop an MAE that is similar in nature that cannot be attributed to any other cause during the 7 days following Vaccination 1.
 - ➤ E-diary data confirmed to be entered in error will not contribute towards a stopping rule.
 - ➤ Unscheduled per-protocol visits to the investigator do not fulfill this criterion unless the event that triggered an unscheduled visit meets the protocol-specified definition of an MAE.
- If any sentinel subject receiving bivalent rLP2086 develops an SAE that cannot be attributed to any other cause within 7 days following Vaccination 1.
- If death occurs in a bivalent rLP2086 recipient during the vaccination period that cannot be attributed to any other cause, or if an investigator determines that the death is related to vaccination.

For each subject, any given event may not contribute more than once to a stopping rule.

The investigator should immediately notify the sponsor if any subject under the investigator's care appears to fulfill any of the criteria listed above. Reporting details are described in the SRM.

The IRC will also consider if local reactions, systemic events, or related AEs have occurred that may jeopardize subject safety.

B1971035

Final Protocol Amendment 2, 19 April 2016

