Two (2) sentinel cohorts, one aged 12 to <15 months and the other aged 18 to <24 months, will each simultaneously and independently enroll approximately 33 subjects. Stopping rules apply for sentinel cohorts (see Section 7.9 Stopping Rules).

60-µg Sentinel Cohort

For each 60-µg dose-level sentinel cohort, approximately 33 subjects will be randomly assigned in a 2:1 ratio to receive either 60 µg of bivalent rLP2086 or HAV vaccine/saline. Stopping rules apply for sentinel cohorts (see Section 7.9 Stopping Rules).

Within the 60-µg sentinel cohort of each age group, when the last subject has received Vaccination 1 and has attended the Day 7 follow-up visit, all post–Vaccination 1, 7-day electronic diary (e-diary) and AE data (summary safety data) will be tabulated for review by the sponsor's IRC.

Following completion of the data review(s) for the 60-µg sentinel cohort, a decision will be made by the IRC whether to proceed to the 120-µg sentinel cohort.

If the IRC finds the 60-µg summary safety data to be acceptable, and no further review is warranted, the subjects in the 60-µg sentinel cohort will continue through the vaccine series.

If the 60-µg summary safety data are unacceptable for the older-age sentinel cohort, then vaccinations will be halted for both of the 60-µg sentinel cohorts and enrollment into the study will stop.

B1971035

Final Protocol Amendment 2, 19 April 2016

If the summary safety data 60-µg dose are acceptable for the older-age sentinel cohort but not the younger-age sentinel cohort, then vaccination and enrollment will cease for the younger-age sentinel cohort only but enrollment may commence for the 120-µg dose-level older-age sentinel cohort only.

120-µg Sentinel Cohort

For each 120-µg dose-level sentinel cohort, approximately 33 subjects will be randomly assigned in a 2:1 ratio to receive either 120 µg of bivalent rLP2086 or HAV vaccine/saline. Stopping rules apply for sentinel cohorts (see Section 7.9 Stopping Rules).

Within the 120-µg sentinel cohort of each age group (if applicable), when the last subject has received Vaccination 1 and has attended the Day 7 follow-up visit, all post–Vaccination 1, 7-day e-diary and AE data (summary safety data) will be tabulated for review by the sponsor's IRC.

Following completion of the sentinel data review(s) of the 120-µg dose, either the 60-µg dose or the 120-µg dose will be selected for each age cohort by the IRC for use in the expanded-enrollment phase of Stage 1.

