3.5. Expanded-Enrollment Phase

3.5.1. 12- to <18-Month Age Stratum

The IRC will review all post–Vaccination 1, 7-day e-diary and AE data obtained from sentinel subjects aged 12 to <15 months. Based on the review, the IRC will select the bivalent rLP2086 dose level to be studied in the Stage 1 expanded-enrollment phase. Younger-age sentinel subjects cannot participate in the 120-µg dose level before the safety data of the 120-µg dose level have been found to be acceptable in the 120-µg older-age sentinel cohort.

The expanded-enrollment phase for this age group will enroll approximately 132 subjects: 66 aged 12 to <15 months and 66 aged 15 to <18 months. Within each of these substratified age groups, subjects will be randomly assigned in a 2:1 ratio to the selected dose level of bivalent rLP2086 or HAV vaccine/saline.

In the event that neither dose level is considered to exhibit a satisfactory safety profile for the 12- to <15-month age group sentinel cohort, expanded enrollment will not commence in the 12- to <18-month age group. So that the study may meet its enrollment numbers, additional enrollment will be permitted in the 18- to <24-month age group.

3.5.2. 18- to <24-Month Age Stratum

The IRC will review all post–Vaccination 1, 7-day e-diary and AE data obtained from sentinel subjects aged 18 to <24 months. Based on the review, the IRC will select the bivalent rLP2086 dose level to be studied in the Stage 1 expanded-enrollment phase.

Once the dose level is selected, an additional approximately 132 subjects aged 18 to <24 months will be enrolled. Subjects will be randomly assigned in a 2:1 ratio to the selected dose level of bivalent rLP2086 or HAV vaccine/saline.

B1971035

Final Protocol Amendment 2, 19 April 2016

3.6. Progression to Stage 2

For all subjects completing Stage 1, a telephone contact will occur at Visit 10 to notify the parent(s)/legal guardian of their child's randomization allocation. Only those subjects who received the 3-vaccination series of bivalent rLP2086 (irrespective of dose level) will continue through Stage 2 to study completion. Subjects who received the 3-vaccination series of HAV vaccine/saline will conclude the study with the Visit 10 telephone contact (Section 6.1.10).

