7.9.1. Resuming Enrollment and Vaccination After a Stopping Rule Is Met

If a stopping rule is triggered by an SAE or death, enrollment and vaccination will not proceed before the IRC receives a recommendation from the EDMC. If a stopping rule is triggered by MAEs, enrollment and vaccination may proceed at the discretion of the IRC before the IRC receives a recommendation from the EDMC.

Once the EDMC has reviewed the AE data and has provided a recommendation to the IRC, the IRC will decide whether or not to continue the study as planned, make changes in study conduct, or stop the study based on the EDMC recommendations. Further information on IRC and EDMC responsibilities and procedures is described in Section 9.4.

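### Protocol 7.9 and 7.9.1 give the hold after a death different scopes, so it is unclear whether a death in an expanded-phase child pauses that child's own cohort

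*Protocol*

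**What the plan says.** Protocol 7.9 opens with a limit. "The study stopping rules (excluding deaths) apply to bivalent" rLP2086 sentinel children, and only in the seven days after Vaccination 1. Deaths are taken out of that limit. The three criteria follow the same pattern. The MAE and SAE criteria are both worded for sentinel children. The death criterion is not: "If death occurs in a bivalent rLP2086 recipient during the vaccination period that cannot be attributed to any other cause". A death that an investigator judges related to vaccination also qualifies.

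Once the IRC confirms that a rule has been met, four actions apply:

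- First: "The dose level affected by the stopping rule will PAUSE enrollment and vaccination in both sentinel age groups".
- Second: "No further study vaccinations will be administered to any subject in the PAUSED sentinel cohorts until directed to do so".
- Third: the EDMC meets, reviews all available safety data and advises the IRC.
- Fourth: "For all sentinel subjects affected by a pause, all other routine study conduct activities" carry on during the pause.

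Protocol 7.9.1, on resuming, makes the IRC wait for the EDMC's advice: "If a stopping rule is triggered by an SAE or death, enrollment and vaccination will not proceed before the IRC receives a recommendation". It states no cohort and no dose level. For an MAE trigger it lets the IRC resume before the EDMC has reported.

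Protocol 3.2.1 and SAP 2.1.2.1 say that stopping rules apply to the sentinel cohorts. The expanded-enrollment sections (Protocol 3.2.2 and 3.5, SAP 2.1.2.2) say nothing about a pause.

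**The concern.** The death criterion was deliberately made wider than the other two, but the actions attached to it were not widened to match. Suppose a child in the expanded phase dies and no other cause is found. The bullets in 7.9 then call for a hold in the sentinel cohorts at that dose and do not mention the cohort in which the death occurred. Whether that cohort is held depends on how 7.9.1 is read.

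What is at stake is the predefined hold on dosing toddlers between IRC confirmation and the EDMC recommendation, after the gravest event that the rules cover. Its scope should not have to be worked out from a subsection heading on the day.

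**Working it through.** **Scopes side by side (Protocol 7.9 and 7.9.1)**

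| Trigger | Who can trigger it | What the 7.9 bullets pause | What 7.9.1 holds until the EDMC advises |
|---|---|---|---|
| Similar MAEs in 2 or more children | Sentinel rLP2086, 7 days after Vaccination 1 | Sentinel cohorts, affected dose | Nothing mandatory; IRC discretion |
| SAE | Sentinel rLP2086, 7 days after Vaccination 1 | Sentinel cohorts, affected dose | Enrollment and vaccination, no scope stated |
| Death | Any rLP2086 recipient, vaccination period | Sentinel cohorts, affected dose | Enrollment and vaccination, no scope stated |

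**Two readings of 7.9.1**

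- *Narrow.* A section on resuming governs only what 7.9 paused. The expanded cohort of the child who died is then not held.
- *Wide.* With no limit stated, everything is held. The same sentence covers SAEs, so one sentinel SAE at one dose would hold every cohort at both doses. That disagrees with the first bullet of 7.9, which pauses one dose level in the sentinel groups.

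Neither reading makes the two sections agree.

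**How many children are involved**

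Inputs: sentinel cohorts of about 33 children, one per dose and age group (3.2.1); expanded cohorts of about 132 per age group (3.2.2); allocation 2:1 throughout.

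- The plan's own total: 4 × 33 + 2 × 132 = 132 + 264 = 396, as in 9.1.
- rLP2086 recipients: 396 × 2/3 = 264. Of these, 132 × 2/3 = 88 are sentinel and 264 × 2/3 = 176 are expanded.
- Share outside the cohorts named in the pause: 176/264 = 67%.

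By dose level, counting rLP2086 recipients only:

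- Same dose chosen in both age groups: 44 sentinel + 176 expanded = 220, the 220 in 9.1. Outside the named cohorts: 176/220 = 80%. Counting controls too, the bullets name 66 of 330 children (20%).
- Doses differ. This can only be 60 µg in the younger group and 120 µg in the older. For a 60-µg death: 44 + 88 = 132, of whom 88 (67%) are outside. For a 120-µg death the younger 120-µg sentinel cohort has been discontinued, leaving 22 + 88 = 110, of whom 88 (80%) are outside.
- Younger group stopped at 60 µg and 165 places moved to the older group (3.3.1): older expanded 132 + 165 = 297, of whom 198 receive rLP2086. With 22 sentinel recipients at the selected dose, 198/220 = 90% are outside.

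**Timing**

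The IRC reviews a sentinel cohort "when the last subject has received Vaccination 1 and has attended the Day 7 follow-up visit" (3.2.1). Under 3.5, "Based on the review, the IRC will select the bivalent rLP2086 dose level to be studied in the Stage 1 expanded-enrollment phase". Two consequences follow.

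- Sentinel children at the selected dose may still be due Vaccinations 2 and 3 when the expanded phase opens. Under the windows in 6.1.4 and 6.1.6 the third dose falls at the latest 70 + 126 = 196 days after the first. The Visit 4 extension or a temporary delay can move it later.
- The younger 120-µg sentinel cohort cannot start until the older 120-µg sentinel data are accepted (3.3.2), and the older expanded cohort also opens on the older sentinel data (3.5.2). Older expanded children can therefore be receiving 120 µg while younger 120-µg sentinel children are still in their 7-day window.

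**The case against.** The strongest reply is that 7.9.1 already gives the protection. Its sentence on SAEs and deaths carries no limit, and taken literally it stops dosing in the expanded phase as well until the EDMC has advised. Other safeguards stand behind it. Investigators notify the sponsor at once of any child who appears to meet a criterion (7.9), and fatal SAEs are reported immediately (8.14.1). The EDMC reviews all available safety data, and the IRC can change or stop the whole study (7.9.1, 9.4). The IRC and EDMC charters, not available here, may say more.

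Much of this stands. A reader might infer that the protocol leaves the expanded cohort running after such a death. The documents do not support that flat reading, because 7.9.1 can be read as a general hold. But that does not settle the matter, since a section on resuming can equally be read as governing only what was paused.

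Two further inferences are tempting and also go too far:

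- *That only the death rule is mismatched.* The SAE trigger and the SAE pause are both limited to sentinel children, so they look consistent. But in the overlap described under Timing, a younger sentinel SAE at 120 µg would, on the narrow reading, leave older expanded children at 120 µg unpaused.
- *That the sentinel pause has little left to hold once the expanded phase is running.* This is true only late in that phase. Early on, sentinel children may still be due two doses, and the younger 120-µg sentinel cohort may still be enrolling.

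**Conclusion.** The point holds as a conflict between two sections of the protocol. The death trigger reaches every rLP2086 recipient, the bullets in 7.9 pause sentinel cohorts only, and 7.9.1 states a hold of undefined scope. It is therefore not clear that a qualifying death in an expanded-phase child pauses that child's own cohort. The SAP does not resolve it.

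In the base plan 67% of rLP2086 recipients are in cohorts that the pause does not name. At a single dose level the share runs from 67% to 90%, depending on dose selection and reallocation. These are planned cohort sizes. They show how far the wording gap reaches; they are not counts of children who would go unprotected, which depends on the reading of 7.9.1 and on when the death occurs.

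The conclusion assumes that the vaccination period in the death criterion covers expanded-phase children. The text supports this, since deaths are exempted from the sentinel limit and the criterion speaks of any recipient. Because the issue is patient safety and the correction is small, it should be made.

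**What to change.** In Protocol 7.9:

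- Amend the first two action bullets. When the death rule is met, enrollment and vaccination pause in all cohorts (sentinel and expanded, both age groups) at least at the affected dose level, until the IRC has the EDMC recommendation. Controls in those cohorts are paused too, because holding only rLP2086 children would reveal allocation. State whether the other dose level is also held.
- In the fourth bullet, drop the word sentinel, so that follow-up continues for every child affected by a pause.

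In 7.9.1, do not narrow the hold after an SAE. Either leave it as written or have the sponsor state its scope, bearing in mind that older expanded children may be receiving 120 µg while younger 120-µg sentinel children are in their 7-day window. If a study-wide hold was always intended, write it into 7.9 so that the two sections agree.

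The cost is three bullets in 7.9 and, if the sponsor chooses, one sentence in 7.9.1. Sample size, endpoints and visits are unchanged. A pause in the expanded phase could push doses past their windows. The Visit 4 extension in 6.1.4 is written for sentinel children awaiting the IRC, so the sponsor may want a matching allowance.
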